9.1 Definition of an Adverse Event

An AE is any untoward medical occurrence in a patient or clinical investigation subject administered a pharmaceutical product and that does not necessarily have a causal relationship with this treatment. An AE can therefore be any unfavorable and unintended sign (including an abnormal laboratory finding), symptom, or disease temporally associated with the use of a medicinal (investigational) product, whether or not related to the medicinal (investigational) product. Examples of an AE include:

- Exacerbation of a pre-existing condition including either an increase in frequency and/or intensity of the condition
- New conditions detected or diagnosed after IP administration even though it may have been present prior to the start of the study.
- Signs, symptoms of a drug interaction

9.2 Definition of Serious Adverse Event

An SAE is any untoward medical occurrence that at any dose:

- Results in death.
- Is life-threatening.

Note: The term “life-threatening” refers to an event in which the subject was at risk of death at the time of the event; it does not refer to an event which hypothetically might have caused death if it were more severe.

- Requires in-patient hospitalization or prolongation of existing hospitalization.
 - a. Hospitalizations for elective surgeries do not constitute an SAE.
- Results in persistent or significant disability/incapacity.
- Is a congenital abnormality/birth defect.

Medical and scientific judgment should be exercised in deciding whether other situations should be considered SAEs, such as important medical events that might not be immediately life threatening or result in death or hospitalization but might jeopardize the subject or might require intervention to prevent one of the other outcomes listed above.

9.3 Disease-Related Events or Outcomes Not Qualifying as AE/SAE’s

Any clinical findings associated with lack of efficacy of the IP are not considered AEs.

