4.4.1 Potential Risks

Potential risks can be categorized as those risks associated with intraocular surgical procedure and those risks associated with the IMP (AURN001).

Potential Risks Associated with Surgery

Potential risks associated with this intraocular procedure include loss of vision, ocular pain and/or discomfort, ocular hyperemia, dry eye, eyelid edema, increased tearing, subconjunctival hemorrhage, corneal or conjunctival abrasion, corneal ulcer, surgical wound leak, shallowing or collapse of the anterior chamber, Descemet's membrane tear, vitreous prolapse, damage to the iris or other structures, changes to the pupil, intraocular bleeding, infection, endophthalmitis, inflammation (uveitis), worsening of corneal edema, posterior capsular opacification (PCO), worsening of cataract, increased IOP, macular edema (including CME and DME), increase in vitreous opacities, posterior vitreous detachment, and retinal detachment, among others.

Potential Risks Associated with the IMP

Potential risks associated with the IMP (AURN001) include ocular pain and/or discomfort, ocular hyperemia, dry eye, failure to improve corneal edema, corneal ulcer, intraocular inflammation (uveitis), infection, endophthalmitis, increased IOP, graft rejection or failure, changes to the pupil, iris or other structures, posterior capsular opacification (PCO), worsening of cataract, increase in vitreous opacities, and macular edema (including CME and DME) among others. Although tumor formation has not been observed in any animal or clinical studies to date, this is a theoretical risk of receiving any cell therapy.

Previous Experience

In prior clinical trials conducted with AURN001 or an earlier formulation in Japan and El Salvador, the most common risks (>5% occurrence) with both the surgical procedure and IMP were as follows:

First In-Human Clinical Trial (Japan)

- Cystoid macular edema (19%)
- Increased IOP (16%)

Other Clinical Trials (Japan)

- Ocular pain (33%)
- Increased IOP (15%)
- Eyelid edema (7%)
- Increased tearing (7%)

Clinical Trials (El Salvador)

- Posterior capsular opacification (PCO) (29%)
- Pupillary disorder (9%)
- Increased IOP (7%)
- Iris disorder (6%)
- Descemet's membrane tear (6%)

Other less common risks (<5% occurrence) included dry eye, blepharitis, macular edema, and anterior chamber inflammation.

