7.1 Inclusion Criteria

Subjects must meet all of the following criteria to be eligible for study participation:

General Criteria:

1. Be 18 years of age or older at the time of signing consent.
2. Able to understand and willing to sign an ICF approved by an Institutional Review Board.
3. Are willing and able to lie face down for approximately 3 hours (± 15 min) immediately after the surgical procedure on Day 1.
4. Are reliable and willing to comply with study instructions and return for all scheduled examinations post-operatively.
5. Women of child-bearing potential must have a negative urine pregnancy test at the Screening Visit and be willing to use birth control, as described below:

All subjects of child-bearing potential, male and female, must agree to use a reliable method of birth control for the entire duration of the study (i.e., 12 months post treatment).

Acceptable methods of birth control include oral contraceptives; implantable contraceptives; injectable contraceptives; a contraceptive patch; barrier methods such as diaphragms with contraceptive jelly, cervical caps with contraceptive jelly, condoms with contraceptive foam, or intrauterine devices; a partner with vasectomy. Birth control is not required if the female is infertile due to surgical sterilization (at least 6 weeks after surgical bilateral oophorectomy, hysterectomy, or at least 6 weeks after tubal ligation) confirmed by medical history or menopause (after at least 12 consecutive months from last menstruation). Post-menopausal females are not required to use birth control.

Men are eligible to participate if they agree to the following for the entire duration of the study (i.e., 12 months post treatment):

- a. Refrain from donating sperm.
- b. For men with partners of childbearing potential or partners who are pregnant or breastfeeding: Use a male condom and should also be advised of the benefit for a female partner to use a highly effective method of contraception as a condom may break or leak when having sexual intercourse with a woman of childbearing potential who is not currently pregnant.

Ocular Criteria in the Study Eye:

6. Have a diagnosis of corneal edema secondary to corneal endothelial dysfunction, requiring surgery (full- or partial-thickness endothelial keratoplasty).
7. Be pseudophakic with a posterior chamber intraocular lens (PC-IOL) located fully within the capsular bag without evidence of zonular instability.

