14.4 Graft Rejection

The Clinical study report will discuss any cases of graft rejection if there are any.

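### The lack-of-efficacy exclusion in Protocol 9.3 has no boundary and overlaps the adverse event definition, so worsening edema or graft failure can be left out of the TEAE and SAE results

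*Protocol*

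**What the plan says.** Protocol 9.1 gives the general definition: "An AE is any untoward medical occurrence in a patient or clinical investigation subject administered a pharmaceutical product", whether or not it is related to treatment. Among its examples is "Exacerbation of a pre-existing condition including either an increase in frequency and/or intensity of the condition". Protocol 9.4.1 requires every AE from Day 1 to Month 12 to be recorded, whatever its severity or relationship.

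Protocol 9.3 then removes a class of findings: "Any clinical findings associated with lack of efficacy of the IP are not considered AEs". That sentence is the whole section. The heading, "9.3 Disease-Related Events or Outcomes Not Qualifying as AE/SAE", carries the rule over to SAEs.

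Protocol 4.4.1 has two risk lists. The product list includes "failure to improve corneal edema, corneal ulcer, intraocular inflammation (uveitis), infection, endophthalmitis, increased IOP, graft rejection or failure". The surgical list includes loss of vision and "inflammation (uveitis), worsening of corneal edema, posterior capsular opacification (PCO".

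TEAEs in Protocol 10.8 and SAP 14.1 are built from recorded AEs. Neither section brings back findings excluded under 9.3.

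**The concern.** Incidence and severity of ocular TEAEs is the first safety evaluation in Protocol 6.2.2. The disease under treatment is an edema that can get worse, and the procedure itself can make it worse. The line between no benefit and harm therefore has to be drawn somewhere, and the protocol does not draw it. Wording that covers any finding associated with lack of efficacy is wider than failure to improve. Two sites could record the same worsening eye differently, and both could cite the protocol.

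Two things are at stake. The first is completeness: an excluded event carries no severity grade and no relationship to product or procedure, and it skips the 24-hour notification in Protocol 9.5 if it would otherwise have been serious. The second is comparison between arms: an arm with more treatment failures has more events open to exclusion. Protocol 4.5 reports that cells given alone showed meaningfully reduced activity in earlier trials, including on need for rescue. The sponsor's own experience thus suggests that failures may not be spread evenly. All five arms have endothelial polishing and one receives no cells. Worsening in that arm might be procedural harm or simply untreated disease.

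**Working it through.** The documents state no figure on this point, so there is nothing to reproduce. The check sets the sections side by side and then asks what happens to an excluded event.

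**1. Does the same event meet both rules?**

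- *Worsening edema.* Under inclusion criterion 6 (Protocol 7.1), every subject must "Have a diagnosis of corneal edema secondary to corneal endothelial dysfunction, requiring surgery". Edema is thus pre-existing in all subjects, and its worsening fits the exacerbation example in 9.1. It can also be read as the product not working, which 9.3 excludes. In 4.4.1 it is a surgical risk, not a product risk.
- *Graft failure.* It is in the product-risk list of 4.4.1. It can equally be read as lack of efficacy under 9.3.
- *Failure to improve.* It is in the product-risk list too, but is plainly lack of efficacy. Leaving it out of AEs is defensible.

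No section says which rule prevails for the first two.

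**2. Where would an excluded event go?**

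- TEAE summaries, the serious-event count and the SAE listing (SAP 14.1): absent, because the event was never recorded as an AE.
- 24-hour SAE notification (Protocol 9.5): not triggered.
- Rescue counts by visit and time to rescue (SAP 14.3): present only if the eye is rescued.
- BCVA loss of at least 15 letters (SAP 14.2): present only if the loss is that large. Entry is allowed down to 5 letters. Assuming a letter score with a floor of 0, an eye starting at 5 can lose at most 5 − 0 = 5 letters, so it cannot meet the criterion; nor can any eye starting below 15.
- Line-loss categories and change in corneal thickness (SAP 13.2), and slit-lamp summaries (SAP 14.5): present, but without severity or relationship.
- Graft rejection (SAP 14.4): "The Clinical study report will discuss any cases of graft rejection if there are any". Graft failure has no named output.
- Data at and after rescue (SAP 7.9): removed from the other efficacy and safety tables. The exception is for AEs, so it helps only if the event was recorded as one.

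**3. Effect on the comparison between arms.** Let *r* be the true proportion of subjects with such an event in an arm, and *c* the chance that an event is classed as lack of efficacy. The expected reported proportion is *r*(1 − *c*), and the expected number lost among *n* subjects is *n·r·c*. If masking makes *c* the same in two arms, the reported difference is (1 − *c*)(*r*₁ − *r*₂). The direction is kept, the difference shrinks, and the arm with the larger *r* loses more events.

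**4. Scale for a single event row, with assumed counts.** About 20 subjects per arm are planned. Exact (Clopper-Pearson) 95% limits are the 0.025 quantile of Beta(*x*, *n* − *x* + 1) and the 0.975 quantile of Beta(*x* + 1, *n* − *x*), with *n* = 20. At *x* = 0 the lower limit is 0.

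| Events in the arm | Row if all are recorded | Row if all are excluded |
|---|---|---|
| 1 | 5% (0.1 to 24.9%) | 0% (0 to 16.8%) |
| 3 | 15% (3.2 to 37.9%) | 0% (0 to 16.8%) |
| 6 | 30% (11.9 to 54.3%) | 0% (0 to 16.8%) |

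The counts are not forecasts, and total exclusion is the extreme case. The table describes one preferred-term row only.

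**The case against.** The strongest reply is that 9.3 is a specific exception following a general definition, so there is no contradiction. That reading is available, and it is why the point is stated as an overlap without a boundary. It does not settle the matter, because an exception still needs an edge. It can also be said that 9.3 speaks of lack of efficacy of the product, so a surgical complication falls outside it. That is reasonable, but it requires the site to know whether post-injection edema came from the surgery or from product failure, which is often the open question.

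The second reply is that most of the signal appears elsewhere. This largely stands: rescue rate and BCVA loss are listed safety evaluations, and corneal thickness and slit-lamp findings are summarized. The loss falls on the AE results, not on the whole safety picture. Safety is also descriptive, with no formal tests, and investigators are masked, which limits arm-dependent classification.

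Three stronger readings may tempt a reader:

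- *Overall ocular TEAE incidence could read 0% when it is really 30%.* Protocol 4.4.1 reports ocular pain in 33%, posterior capsular opacification in 29% and raised IOP in 7 to 16% of earlier subjects. Overall incidence would not be expected to be zero.
- *Graft rejection depends on AE capture and could vanish.* Rejection is its own safety evaluation with its own SAP section. The CRF is not in the documents, so dependence on AE capture cannot be shown.
- *Weaker arms would look safer overall.* With equal classification across arms, the difference in that row shrinks but does not reverse, and failures still show in rescue and vision loss.

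**Conclusion.** The point holds as a definitional overlap with a real but partial consequence. Worsening beyond baseline and graft failure can be left out of the TEAE and SAE results and of expedited SAE reporting, and more such events would be lost where treatment fails more often.

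The size is unknown. It depends on how often these events occur and how sites classify them, and the documents give neither. The arm-level argument assumes unequal failure rates, which Protocol 4.5 suggests but does not establish for this trial. It also assumes masked classification that is similar across arms; if classification differed by arm, the direction of the effect could not be predicted.

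The point merits correction because the gap affects a leading safety measure and can be closed with little text. It does not show that the trial's safety conclusions would be wrong.

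**What to change.** Reconcile Protocol 9.1, 9.3 and 4.4.1:

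- Limit 9.3 to failure to improve from baseline.
- State that worsening beyond baseline, graft failure and graft rejection are assessed under 9.1 and 9.2, and recorded accordingly, regardless of presumed lack of efficacy.
- Note that failure to improve remains in 4.4.1 as a disclosed risk, so that its listing there is not taken to make it an AE.

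What counts as worsening beyond baseline is for the sponsor to define. The SAP's TEAE definition needs no change, since it takes whatever the sites record.

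The text change is short, but it is a protocol amendment and needs IRB or ethics approval before use (Protocol 13), plus a note to sites. Reported ocular AE counts will rise somewhat. Events already left unrecorded under the current wording also need a check; otherwise the trial will have two capture rules. BCVA, corneal thickness, slit-lamp and rescue data already collected can guide that check, and it should be done without reference to treatment assignment.

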9.4 Monitoring and Recording of AEs and SAEs

9.4.1 Adverse Events

Any AE experienced by the subject from Visit 2 (Day 1) through Visit 10 (Month 12) is to be recorded in the eCRF, regardless of the severity of the event or its relationship to study treatment.

Any AEs already documented at a previous assessment and designated as ongoing, should be reviewed at subsequent visits as necessary. If these have resolved, this should be documented.

Changes in intensity or frequency of AEs should be recorded as separate events (i.e., a new record started).

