9.7 Evaluating AEs and SAEs

9.7.1 Severity

The following definitions should be considered when evaluating the severity of AEs and SAEs.

Mild	Event is noticeable to the subject, but is easily tolerated and does not interfere with the subject's daily activities
Moderate	Event is bothersome, possibly requiring additional therapy, and may interfere with the subject's daily activities
Severe	Event is intolerable, necessitates additional therapy or alteration of therapy, and interferes with the subject's daily activities.

For AEs that change in intensity, the start and stop date of each intensity should be recorded.

An AE that is assessed as severe should not be confused with a SAE. An event is defined as 'serious' when it meets one of the pre-defined outcomes as described in Section 9.2 Definition of a SAE.

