10.8 Safety Analyses

All safety analyses will be conducted on the Safety Analysis Set. No formal statistical tests of treatment difference are planned.

AEs will be coded using the Medical Dictionary for Regulatory Activities TEAEs (i.e., AEs that begin or worsen in severity after initiation of study drug) will be summarized by treatment arm and overall, in the study eye. Non-ocular TEAEs will also be summarized. Additionally, TEAEs and serious AEs will be summarized in a similar manner by maximum severity and relationship to study drug and the surgical procedure.

Changes from baseline of quantitative measurements (ophthalmic evaluations, laboratory findings) will be summarized by treatment arm and timepoint.

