14 SAFETY ANALYSES

14.1 Adverse Events

Adverse events will be coded using Medical Dictionary for Regulatory Activities (MedDRA) version 26.1.

Treatment-emergent adverse events (TEAEs) are defined as any adverse events that occur during or after the Day 1 injections, or any adverse events that are continuous from the screening but worsen during or after the Day 1 injections.

Ocular and non-ocular TEAEs will be summarized separately. Summary of ocular TEAEs will be separated by study eye and non-study eye.

An overall summary including the number of events and the number and percentage of subjects who experienced at least one TEAE will be presented by treatment group and overall. The overall summary will also include at least one serious TEAE, treatment-related TEAE, treatment-related serious TEAE, TEAE leading to subject discontinuation from the study, and TEAE leading to death.

TEAEs will be summarized by System Organ Class (SOC) and Preferred Term (PT). Subjects are counted only once under each SOC or PT for which they have at least one TEAE.

Summaries by relationship to study product, by relationship to study procedure and by maximum severity will also be provided.

Serious TEAEs will not be summarized in table format as it is anticipated number of serious TEAEs will be very limited.

In addition, the following AE summaries will be provided for AEs collected at and after rescue visits:

- Overall summary of TEAE
- TEAE by SOC and PT

For these summaries, denominators to be used for percentage calculation will be number of Rescued subjects.

All AEs will be presented in a subject listing with a flag indicating TEAE and a flag indicating AEs occurred at and after rescue visits. In addition, all serious AEs will be presented in a separate listing.

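### Every change in AE grade or frequency opens a new record, and the SAP has no rule to count one episode once, either in event totals or in the post-rescue TEAE tables

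*Protocol*

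**What the plan says.** **Recording.** Protocol 9.4.1: "Changes in intensity or frequency of AEs should be recorded as separate events (i.e., a new record started"). Protocol 9.7.1 adds: "For AEs that change in intensity, the start and stop date of each intensity should be recorded". On resolution, 9.4.1 says only "If these have resolved, this should be documented", so resolution closes a record and opens none.

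**Definition of a TEAE.** SAP 14.1: "Treatment-emergent adverse events (TEAEs) are defined as any adverse events that occur during or after the Day 1 injections". The second part of the definition covers "any adverse events that are continuous from the screening but worsen during or after the Day 1 injections". The worsening condition therefore applies only to events carried over from screening. Protocol 10.8 is narrower and limits TEAEs to "AEs that begin or worsen in severity after initiation of study drug".

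**Counting.** SAP 14.1 plans "An overall summary including the number of events and the number and percentage of subjects who experienced at least one TEAE". In the SOC and preferred-term tables a subject counts once per term, and severity is summarised at its maximum.

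**After rescue.** SAP 14.1 also states that "the following AE summaries will be provided for AEs collected at and after rescue visits": an overall TEAE summary and a SOC/PT table, with rescued subjects as the denominator. SAP 7.9 keeps data from the rescue visit onward out of the other safety tables.

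**The concern.** The recording rule suits a listing, where the reader wants the course of each event. It does not suit a count. If the analysis takes each record as an event, the event total reflects both how many episodes occurred and how often they were re-graded. Two arms with the same number of episodes could then show different totals only because events in one arm fluctuated more.

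The post-rescue tables raise a separate problem. Records enter them according to when they were collected. An AE that began before keratoplasty and steps down a grade afterwards produces a record dated after rescue. Counting each subject once gives no protection, because that record may be the subject's only entry for the term in that table. Here the subject percentage itself can be wrong, on a small denominator.

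Safety is the trial's secondary objective and no formal safety tests are planned (Protocol 5 and 10.8), so these descriptive tables are the safety evidence that readers will use.

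**Working it through.** The plan states no figure that could be reproduced here. The check traces the written rules and then shows how the counts behave.

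**Inputs from the documents**
- A new record at each change in intensity or frequency, in either direction (Protocol 9.4.1); none at plain resolution (same section).
- Any AE on or after the Day 1 injection is a TEAE; the number of events is reported; no linking rule is stated (SAP 14.1).
- Post-rescue tables use rescued subjects as the denominator (SAP 14.1).
- About 20 subjects per arm (Protocol 6.1).

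**Assumed, because the documents do not give them:** the rate of grade changes and the number of rescued subjects.

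**Step 1: records per episode.** Records = 1 + k, where k is the number of changes.

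| Course of one episode | k | Records as written | Counted once per episode |
|---|---|---|---|
| moderate, resolved | 0 | 1 | 1 |
| moderate, mild, resolved | 1 | 2 | 1 |
| mild, moderate, severe, moderate, mild, resolved | 4 | 5 | 1 |

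If only worsening opened a new event, the last row would give 1 + 2 = 3.

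**Step 2: event total in an arm.** Assume 20 subjects with one episode each and a mean of m changes per episode. Events = 20 × (1 + m).
- m = 0: 20 × 1 = 20
- m = 0.5: 20 × 1.5 = 30
- m = 1: 20 × 2 = 40
- m = 2: 20 × 3 = 60

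The number of subjects with a TEAE is 20 in every case. An arm at m = 1 beside an arm at m = 0 would show 40 events against 20 with the same number of episodes.

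**Step 3: records opened at or after rescue.** In the second row of the table, with rescue falling between moderate and mild, 1 record is opened after rescue. In the third row, with rescue after the severe grade, 2 are. In the first row, none is.

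**Step 4: post-rescue percentage.** One subject whose only post-rescue entry is a downgrade adds 100 / R percentage points, where R is the number of rescued subjects in the column.
- R = 2: 50
- R = 4: 25
- R = 6: 16.7
- R = 10: 10

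**Step 5: under the proposed rule.** Every episode in Step 1 counts as 1. The downgrade-only records in Step 3 add 0 to the post-rescue tables instead of 1 and 2.

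**The case against.** The strongest reply is that the SAP never says a record is an event. It is silent on collapsing, and a programming specification outside these documents could link records. That stands: counting each record is an inference from the absence of a rule.

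The documents also lean against treating an improvement as a TEAE. Protocol 9.1 defines an AE as untoward and gives an increase in frequency or intensity as its example. Protocol 10.8 requires onset or worsening, and SAP 15 declares no departure from the protocol's analyses. This helps but does not settle the matter. A new record carries its own start date, Protocol 9.4.1 itself calls it a separate event, SAP 14.1 is worded more broadly, and SAP 2 gives the SAP precedence on methods. The listing flag in SAP 14.1 refers to AEs that occurred, not were collected, from the rescue visit onward. That could mean assignment by onset, but the table rule uses the other word.

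A reader might infer that recovery from the condition that led to rescue would be reported as a new post-rescue TEAE. The documents do not support this in general. Protocol 9.3 excludes findings of lack of efficacy from AEs, so edema that persists because treatment failed has no AE record to re-grade. Only other AEs ongoing at surgery are exposed. Follow-up after rescue is about one month (Protocol 8.3), which limits how many will change grade. The severity scale has three broad grades, so re-grading may also be infrequent.

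A reader might also infer that AE incidence by arm is inflated. It is not: subjects count once per term, and severity is taken at its maximum.

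**Conclusion.** The point holds in a limited form. As written, the recording rule and the TEAE definition let one episode count several times in the overall summary's event totals. They also let an AE already ongoing at rescue appear among post-rescue TEAEs when it has only eased. The first effect is confined to event counts, which are printed beside unaffected subject counts. The second can reach subject percentages, but only in the supplementary post-rescue tables, and only for AEs that change grade or frequency without simply resolving.

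The conclusion rests on the absence of a linking rule in the SAP and on reading the post-rescue criterion by date of collection. No actual amount of inflation can be stated. The ranges of 20 to 60 events per 20 episodes, and of 50 to 10 percentage points for 2 to 10 rescued subjects, follow from assumed inputs and are not predictions. No efficacy result and no main-table subject-level safety result is at risk. The change is still worth making, because the rule as written gives a less meaningful count than a cheap alternative that also agrees with the protocol's own TEAE wording.

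**What to change.** Leave Protocol 9.4.1 as it is, and use the individual records for listings. Add to SAP 14.1:

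1. An event is one continuous episode. Link contiguous records of the same subject, eye and preferred term, or use a link field in the eCRF. Count the episode once, at its onset date and maximum severity.
2. A record opened only because intensity or frequency fell is not a new TEAE.
3. An episode enters the post-rescue tables only if its onset, or a worsening, is at or after rescue.

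The cost is SAP wording, one programming step and, if chosen, one eCRF field. The drawback is that two truly separate back-to-back events of the same term could be merged. A listing of merged records without treatment codes can catch this. Because SAP 7.1 unmasks the sponsor for the Month 6 report, the linking rule should be fixed before then, and later merges should still be checked on listings without treatment codes.
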